#### 5.2.3.2. 30-Day Post-Surgery Visit (Study Day 43 to Day 48 [ $\pm 3$ days])

Subjects will undergo the following evaluations.

1. Vital signs (pulse, blood pressure, temperature, and respiration rate).
2. ECOG Performance Status.
3. Chest CT scan.
4. Serum  $\beta$ -HCG (only for female subjects of childbearing potential).
5. Record the result of the Light Challenge.

6. Re-educate the subject on how to manage light exposure based on the result of the Light Challenge.
  - If the subject passes the Light Challenge, the subject will be instructed to gradually resume normal outdoor activities, initially continuing to exercise caution and gradually allowing increased exposure.
  - If the subject does not pass the Light Challenge, the subject will be instructed to continue adhering to light restrictions and repeat the Light Challenge in 14 days. The Light Challenge should be repeated every 14 days until passed.
7. Record concomitant medications and adverse events.

#### *5.2.3.3. 90-Day Post-Surgery Last Study Visit (Study Day 103 to Day 108 [ $\pm 7$ days])*

Subjects will undergo the following evaluations.

1. Vital signs (pulse, blood pressure, temperature, and respiration rate).
2. Comprehensive Physical Examination.
3. ECOG Performance Status.
4. CT scan and evaluation.
5. Clinical labs (Appendix 13-4).
6. Serum  $\beta$ -HCG (only for female subjects of childbearing potential).
7. Re-educate the subject on how to manage light exposure, if needed.
8. Record concomitant medications and adverse events.

### 5.3. End-of-Study Procedures

#### 5.3.1. Subjects who completed the study

For subjects who complete this study, no additional post-treatment follow-up visits are required.

Any subject with a clinically significant abnormal laboratory value, a continuing adverse event judged to be associated with treatment, or a continuing serious adverse events will be followed according to accepted medical standards until all parameters, including laboratory values, have either returned to normal or to the baseline value or are otherwise explained or judged acceptable by the investigator. Subjects with continuing abnormalities/events should be discussed with the sponsor to ensure appropriate management and follow-up.

#### 5.3.2. Subjects who prematurely discontinued the study

##### *5.3.2.1. Early discontinuation due to consent withdrawal*

In case of withdrawal of consent, the date of withdrawing consent will be collected. If possible, the reason for withdrawing consent will be collected to exclude safety reason. No additional data will be collected from the time of consent withdrawal.

*5.3.2.2. Early discontinuation for reason other than withdrawing consent*

The investigator will make every effort to complete the following at the time of study discontinuation.

1. Reason for early discontinuation.
2. Comprehensive Physical Examination.
3. Vital signs (pulse, blood pressure, temperature, and respiration rate).
4. ECOG Performance Status.
5. Clinical labs (Appendix 13-4).
6. Serum  $\beta$ -HCG (only for female subjects of childbearing potential).
7. Concomitant medications and adverse events.

---

## 6. MATERIALS

### 6.1. Photofrin®

#### 6.1.1. Supply

Photofrin® 75 mg (porfimer sodium) for injection will be supplied by Concordia Laboratories Inc. (St. Michael, Barbados).

#### 6.1.2. Packaging and Labelling

##### 6.1.2.1. Primary Packaging (Vial)

A label will be affixed to each vial. The label will comply with local regulations and will reflect the following, but not be limited to, pertinent study information: pharmaceutical dosage form, route of administration, the name/identifier and strength/potency, protocol number, lot number, re-assay/expiry date, subject number (or space provided), investigator name (or space provided), sponsor identification, storage conditions.

##### 6.1.2.2. Secondary Packaging (Carton)

A label will be affixed to each carton. The label will comply with local regulations and will reflect the following, but not be limited to, pertinent study information: pharmaceutical dosage form, route of administration, the name/identifier and strength/potency, protocol number, lot number, re-assay/expiry date, subject number (or space provided), investigator name (or space provided), sponsor identification, storage conditions, caution statement, direction for use.

#### 6.1.3. Reconstitution and Administration of Photofrin®

##### 6.1.3.1. Reconstitution

Reconstitute each 75-mg vial of Photofrin® with 31.8 mL of 5% Dextrose Injection (USP) which will result in a final concentration of 2.5 mg/mL. Shake well until dissolved. Do not mix Photofrin® with other drugs in the same solution. Porfimer sodium, reconstituted with 5% Dextrose Injection, has a pH in the range of 7 to 8 and has been formulated with an overage to deliver the 75 mg labeled quantity.

The reconstituted product should be protected from bright light and used immediately. Reconstituted Photofrin® is an opaque solution, in which detection of particulate matter by visual inspection is extremely difficult. Reconstituted Photofrin®, however, like all parenteral drug products, should be inspected visually for particulate matter and discoloration prior to administration whenever solution and container permit.

##### 6.1.3.2. Administration

Photofrin® dose will be 2 mg/kg body weight.

For conversion from subject's weight in pounds to kilograms multiply by 0.454 (e.g., 200 lbs x 0.454 = 91 kg).

The “mg/kg” will be converted in “mL” to be administered as follows:

$$\text{Total volume of Photofrin}^{\text{®}} \text{ (mL)} = \frac{\text{Subject's weight (kg)} \times 2 \text{ mg/kg}}{2.5 \text{ mg/mL}}$$

#### **6.1.3.3. Spillage and Disposal**

Any spillage of Photofrin® should be wiped up with a damp cloth. Contact to the skin and eyes should be avoided due to the potential of photosensitivity reactions upon exposure to light. It is recommended that rubber gloves and eye protection be used. All contaminated materials should be disposed of in a polyethylene bag in compliance with local regulations.

#### **6.1.3.4. Study Drug Dosing Compliance**

Assessment of compliance with the dosing regimen is not applicable as Photofrin® will not be provided to subjects for self-administration. Any variance of administration with the intended dose will be recorded.

#### **6.1.3.5. Storage, Dispensing and Reconciliation**

Prior to reconstitution, vials must be stored at controlled room temperature of 20°C-25°C (68-77°F) in a secure, locked facility accessible only to the investigator or authorized personnel. The vial must be kept in the carton until its used. Reconstituted solutions must be protected from bright light and used immediately. The storage area must be free of environmental extremes. Prior to the study start, the drug storage area will be inspected by a Concordia Laboratories Inc. monitor or designee.

A qualified individual (pharmacist or authorized study personnel) designated by the investigator will dispense Photofrin® only to subjects enrolled in this study. Photofrin® supplies must not be loaned or dispensed by the investigator to another investigator or site or used for any purpose other than the study.

Upon receiving Photofrin® supplies, the qualified individual must complete, sign and return to the sponsor the form acknowledging the receipt of Photofrin®. Each box will be identified by a reference number, which will be recorded in the inventory/dispensing record to document its use per subject. It is the responsibility of the qualified individual designated by the investigator to maintain and keep current the inventory/dispensing record for all drugs withdrawn and dispensed. A copy of the Photofrin® inventory/dispensing record must be kept at the investigator's site and be available to the sponsor's monitor or designee who will visit the site. Any discrepancy and deficiency are to be recorded and explained.

## **6.2. Optical Fibers**

### **6.2.1. Supply**

Sterile Optiguide™ cylindrical diffusers (DCYL700 series) manufactured for Concordia Laboratories Inc. are available in several lengths for single use and will be supplied in sufficient quantities to allow for the treatment of subjects on the study. The choice of the diffuser length

will depend on the length of the tumor to avoid exposure of nonmalignant tissue to light and to minimize overlapping of previously treated malignant tissue.

#### 6.2.2. Packaging and Labelling

Labeling of the primary and secondary packaging will comply with all local regulations of the receiving country.

Optical fibers will be mechanically protected in a dispenser tray. The primary packaging will consist of a sealed pouch. The loaded tray will be placed into the pouch. The secondary packaging will consist of an individual box and will contain the primary packaging and the instructions for use. A label will be affixed to the primary and secondary packaging. The label will comply with local regulations and will reflect the following, but not be limited to, pertinent study information: device name/identifier, protocol number, subject number (or space provided), investigator name (or space provided), lot number, re-assay/expiry date, caution statement as per local regulations, manufacturer or manufactured for identification, storage conditions.

#### 6.2.3. Storage, Dispensing, and Reconciliation

Optical fibers must be stored in its original individual box and in a secure, dry location, away from temperature extremes, accessible only to authorized study personnel.

Upon receiving the optical fibers, the authorized study personnel will complete, sign and return to the sponsor the form acknowledging the receipt of the optical fibers. Each optical fiber will be identified by a reference number, which will be recorded in the inventory/dispensing record to document its use per subject. A copy of the device inventory/dispensing record must be kept at the study site and be available to the sponsor's monitor or designee who will visit the site. Any discrepancies and deficiencies are to be recorded.

Optical fibers must not be loaned or dispensed by the investigator to another investigator or site or used for any purpose other than the study.

#### 6.2.4. Inspection of Optical Fibers

Fiber optic diffusers must be checked for gross defects, proper functioning and power output prior to use. Optical fibers should visually be inspected by placing the optical fiber into the laser calibration port. Using the trace light emitted during about 10-20 sec when the laser is preparing for calibration, the fiber can be inspected for irregularities such as "hotspots" or nicks in the cylinder or coating on the fiber itself, which would interfere with the proper administration of the light dose. If such defects are detected a new fiber should replace the defective fiber. Likewise, the new fiber must be tested for defects prior to use. In the event of damage, the damaged optical fiber diffuser must be returned to the sponsor using the provided event form.

---

### 6.3. Disposition of Photofrin® and Optical Fibers

During the study, the sponsor's monitor or designee will periodically check the inventory/dispensing record for the complete accountability of Photofrin® vials and optical fibers. At the end of the study, the sponsor's monitor or designee will perform a last check of the inventory/dispensing record. Any discrepancies will be explored and documented.

#### 6.3.1. Disposition of Unused Photofrin® and Optical Fibers

At the end of the study, all unused Photofrin® vials and optical fibers, along with the inventory/dispensing records, will be returned to the sponsor or designee who will perform the final reconciliation; any discrepancies will be explored and documented.

The sponsor may grant permission for the destruction of unused Photofrin® vials on site. In such case, Photofrin® vials shall be disposed as per institution's guidelines for biohazard medical waste with written documentation. The record shall include the following:

- A copy of the institution's Standard Operating Procedures;
- The name and signature of the person who destroyed the supplies;
- The identity and quantity of destroyed product;
- Method and date of destruction.

A copy of the destruction record will be provided to the sponsor.

#### 6.3.2. Disposition of Used Photofrin® and Optical Fibers

All used Photofrin® vials and optical fibers shall be disposed as per institution's guidelines for biohazard medical waste with written documentation. The record shall include the following:

- A copy of the institution's Standard Operating Procedures;
- The name and signature of the person who destroyed the supplies;
- The identity and quantity of destroyed product;
- Method and date of destruction.

A copy of the destruction record will be provided to the sponsor.

---

## 7. WARNINGS AND PRECAUTIONS

### 7.1. Phototoxicity Reactions

All subjects who receive Photofrin® will be photosensitive and must observe precautions to avoid exposure of eyes and skin to direct sunlight or bright indoor light (from examination lamps, including dental lamps, operating room lamps, unshaded light bulbs at close proximity, etc.) for at least 30 days or longer as per local labelling.

The level of phototoxicity will vary for different areas of the body, depending on the extent of previous exposure to light. Before exposing any area of skin to direct sunlight or bright indoor light, the subject should perform the Light Challenge to test the skin for residual phototoxicity. A small area of skin (e.g., hand) should be exposed to sunlight for 10 minutes. If no phototoxicity reaction (erythema, edema, blistering) occurs within 24 hours, the subject can gradually resume normal outdoor activities, initially continuing to exercise caution and gradually allowing increased exposure. If a phototoxicity reaction occurs with the limited skin test, the subject should continue the existing precautions for another 2 weeks before re-testing. As the tissue surrounding the eyes may be more sensitive, it is therefore not recommended that the face be used for testing. If subjects travel to a different geographical area with greater sunshine, they should retest their level of phototoxicity. Ultraviolet (UV) sunscreens are of no value in protecting against phototoxicity reactions because photoactivation is caused by visible light.

Some subjects may remain photosensitive for up to 90 days or more. The photosensitivity is due to residual drug, which will be present in all parts of the skin. Exposure of the largest possible area of skin to ambient indoor light is, however, beneficial because the remaining drug will be inactivated gradually and safely through a photobleaching reaction. Therefore, subjects should not stay in a darkened room during this period and should be encouraged to expose their skin to ambient indoor light.

### 7.2. Ocular Sensitivity

Ocular discomfort, commonly described as sensitivity to sun, bright lights, or car headlights, has been reported in subjects who received Photofrin®. Subjects should wear dark sunglasses when outdoors, which have an average white light transmittance of < 4% for at least 30 days or longer as per local labelling. Subject should be advised to consult their ophthalmologist if they notice any change in vision after PDT.

### 7.3. Training and Instructions

Members at each site will be trained by the sponsor-designated representatives to ensure knowledge of subject safety issues prior to recruitment of the first subject. All subjects will be seen in clinic prior to scheduling the procedure and will be educated on the risks and benefits of the intervention and educated on the preventive measures to avoid cutaneous phototoxicity. Subjects will also be given a "Patient Kit", which includes gloves, sunglasses, hat with neck protection, and instructions on how to manage light exposure. Subjects will be encouraged to

[figure not shown]
expose their skin to ambient indoor light. Subjects will not be considered for the study if the clinician deems that the subject is not mentally capable of following instructions to prevent phototoxicity.

## 8. ASSESSMENT OF SAFETY

Any adverse event/concurrent illness experienced by a subject during any portion of the study must be described in detail and be fully evaluated by the investigator. The investigator is responsible for recording and reporting all adverse events observed or reported during the study from informed consent signature until date of completion/discontinuation, regardless of drug-related assessment and/or clinical significance. Any pertinent information must be recorded in the Case Report Form (CRF) and additional comments describing the course and outcome of these events should be provided as appropriate.

### 8.1. Definitions

An **Adverse Event (AE)** is defined as any untoward medical occurrence in a subject or clinical investigation subject during the course of a clinical study regardless of the causal relationship. The following flow chart illustrates the decision-making process the investigator should follow in determining how to document an AE in the study.

An **Unexpected Adverse Event** is defined as an adverse drug event, the nature or incidence of which is not consistent with the Investigator Brochure.

---

A **Serious Adverse Event (SAE)** is defined as any untoward medical occurrence that at any drug dose:

- Results in death;
- Is life-threatening;
- Requires inpatient hospitalization or prolongation of existing hospitalization excepting hospital admissions due to administrative reasons (e.g., the subject has no transportation home) or hospitalization for elective treatment of a pre-existing condition that did not worsen during the study unless a complication occurs during the hospitalization;
- Results in permanent or significant disability/incapacity; or
- Results in congenital anomaly/birth defect.

Other important medical adverse events may also be considered serious, depending on the judgment of the investigator or the sponsor (e.g., from ICH guidelines, intensive treatment in an emergency room or at home to prevent one of the outcomes listed in this definition, blood dyscrasias or convulsions that do not result in hospitalization or development of drug dependency or drug abuse). In addition, suspected transmission of infectious agents should always be considered as a SAE.

Note that as defined, serious events (expected or not) are not necessarily causally associated with the study treatment.

## 8.2. Pre-existing Medical Conditions

Any pre-existing medical condition (including findings from physical examination), which does not worsen in duration, intensity or frequency during the study, is not an AE. These pre-existing medical conditions should be adequately documented in the medical history/current illnesses of the CRF and any other appropriate ancillary documents. Pre-existing medical conditions which worsen after ICF signature will be recorded as an AE on the Adverse Event Form of the CRF.

## 8.3. Laboratory Abnormalities

During the course of the study, the investigator will be required to comment on any laboratory values outside the normal reference range. A laboratory abnormality should be regarded as an AE and recorded on the Adverse Event Form of the CRF if, per the investigator's judgment, the value is significantly worse than at pretreatment (where "significantly worse" is defined as Grade 3 or 4 by the CTCAE) and has been confirmed by repeat testing, when applicable. In addition, a clinically significant abnormal laboratory test value discovered after ICF signature and that was not previously known should be considered as an AE.

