#### 4.3.2. Exclusion Criteria

Potential subjects who meet any of the exclusion criteria will not be allowed to enroll into the study.

1. Subject diagnosed with small cell lung cancers or carcinoid tumors.
2. Subject has a primary or metastatic lung tumor located within 2 cm of the proximal bronchial tree or within 2 cm of a major structure (e.g., aorta, heart, trachea, pericardium, superior vena cava, pulmonary artery, pulmonary vein, esophagus, spine).
3. Subject has a primary or metastatic lung tumor near the vertebral body.
4. The tumor invades a major blood vessel.
5. Subject with concurrent non-solid malignancy.
6. Subject has had previous direct radiation treatment (other than mediastinal radiation) on the tumor scheduled for resection.
7. Subject has had chemotherapy in the last four weeks.
8. Subject has received prior PDT on the tumor scheduled for resection during 3 months prior to the date of the ICF signature.
9. Subject with blood parameters of Grade 3 or higher on the Common Terminology Criteria for Adverse Events (CTCAE) 5-point scale; parameters of Grade 2 will be excluded if judged clinically significant by the investigator.
10. Subject with known porphyria or known hypersensitivity to Photofrin® or porphyrin-like compounds or to any of its excipients.
11. Subject with a coexisting ophthalmic disease likely to require slit-lamp examination within the next 90 days.
12. Subject with any acute or chronic medical or psychological illnesses as judged clinically significant by the investigator to preclude bronchoscopy procedures.
13. Female subject who is breastfeeding or intends to breastfeed during the study.
14. Subject who participated within the last 30 days, participates or intends to participate in another investigational study (other than observational studies) during the study.

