#### 8.4.1. Assessment and Recording

An AE, whether or not considered to be causally related to the treatment, must be promptly documented and recorded. At each study visit, after the subject has had an opportunity to spontaneously mention any problems, the investigator should inquire about AEs by asking the appropriate open questions. In addition to straightforward subject observation (e.g., headache, nausea, etc.), AEs will also be documented from any data collected in the CRF (e.g., laboratory values, physical examination findings, ECG changes, etc.) or other documents that are relevant to the safety of the subject.

At each follow-up visit or assessment by phone or otherwise, all AEs, whether observed by the investigator or other professional collaborators, or reported by the subject spontaneously or in response to an open question, will be recorded on the Adverse Event Form included in the CRF with the following information.

- Name of the AE: Name should be a medical term. When possible, the investigator should differentiate an illness entity from isolated symptoms or signs. For instance, the term “flu” should be recorded instead of listing all the flu-related symptoms. Where a differentiation is not possible, symptoms and signs should be separately recorded and evaluated as adverse events.
- Date of onset of the AE.
- Intensity: Event intensity will be assessed according to the CTCAE. If not described in the CTCAE, the intensity should be assessed according to the following categories: *Mild* (noticeable to the subject, does not interfere with the subject’s daily activities, usually does not require additional therapy, dose reduction, or discontinuation of the study); *Moderate* (interferes with the subject’s daily activities, possibly requires additional therapy, but does not require discontinuation of the study); *Severe* (severely limits the subject’s daily activities and may require discontinuation of the study); *Life-threatening*; *Death*.
- Date of resolution (or statement that the event is continuing).
- Action taken (e.g., concomitant medication or adjunctive therapy given will be recorded on the Concomitant Medications Form or the Adjunctive Therapy Form of the CRF, respectively).
- Outcome defined as resolved, resolving, ongoing, worsening, death, or unknown.
- Whether the event meets the definition of a SAE (see Section 8.1).

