5.4.11.2 Clinical Laboratory Parameters

Samples will be obtained for the clinical laboratory tests at the following time points: Screening, Hospital Discharge (Day 5) and Study Exit visits.

The following tests will be performed:

- Chemistry: Glucose (random), Blood urea nitrogen, Sodium, Potassium, Chloride, Creatinine, Alkaline Phosphatase, Aspartate Aminotransferase, Alanine Aminotransferase, Total bilirubin, Albumin, Total protein.
- Hematology: Hemoglobin, Hematocrit, White blood cell, Red blood cell, Platelet count, Prothrombin time

Additionally, samples for Serum β -HCG pregnancy test will be collected from women of childbearing potential only at Screening, Day 43-48 visit and Study Exist visit.

Laboratory results for chemistry and hematology as well as changes from baseline will be summarized descriptively by visit. Only subjects with both non-missing baseline and time point values will be summarized at each time point.

Shifts among normal, low and high results (as determined by laboratory normal ranges) from baseline to last available post-baseline assessment will be summarized.

All individual subject clinical laboratory results will be presented in listings by subject and visit. Results of the pregnancy test will be listed.

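### Protocol 8.3, read on its own, can leave a clinically significant worsening of an already known laboratory abnormality unrecorded as an AE if it stays below Grade 3

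*Protocol*

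**What the plan says.** Protocol 8.3 makes a laboratory abnormality an AE by two routes.

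- **Route 1, worsening.** In the investigator's judgment the value is significantly worse than the pretreatment value, and it is confirmed by a repeat test where that applies. That degree of worsening "is defined as Grade 3 or 4 by the CTCAE".
- **Route 2, new finding.** "a clinically significant abnormal laboratory test value discovered after ICF signature and that was not previously known should be considered as an AE".

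The surrounding text is broader. The opening of Section 8 makes the investigator responsible for recording every AE from consent onward, whatever its clinical significance. Section 8.1 defines an AE as "any untoward medical occurrence in a subject or clinical investigation subject during the course of a clinical study regardless of the causal relationship". Section 8.4.1 adds that "AEs will also be documented from any data collected in the CRF (e.g., laboratory values" and other examples in the same parenthesis. Section 8.2 says: "Pre-existing medical conditions which worsen after ICF signature will be recorded as an AE on the Adverse Event Form of the CRF". It speaks of medical conditions and physical examination findings, and does not name laboratory values.

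On entry, exclusion criterion 9 (Protocol 4.3.2) bars blood parameters of Grade 3 or higher and adds that "parameters of Grade 2 will be excluded if judged clinically significant by the investigator". Grade 1 values, and Grade 2 values not so judged, may therefore be present at baseline.

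AE incidence is the primary endpoint (Protocol synopsis; SAP 4.1). SAP 5.4.11.1 attaches a one-sided 95% exact upper limit to each AE percentage. SAP 5.4.11.2 summarises laboratory results and changes from baseline by visit, lists all individual results, and tabulates "Shifts among normal, low and high results (as determined by laboratory normal ranges") from baseline to the last available post-baseline assessment.

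**The concern.** Route 1 is introduced as a comparison with pretreatment but is decided by an absolute grade. Route 2 is open to lower grades but carries a novelty condition. Between them lies a known, mild abnormality that becomes clinically significant without reaching Grade 3. Two subjects with the same value after PDT may then be classified differently because one of them was already abnormal at screening.

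Any such loss runs in one direction, toward fewer AEs, in a study whose primary objective is safety. With about five sites and ten subjects, a rule that can be read in two ways may also make AE counts depend on the site. That works against the aim of consistent assessment stated at the start of Protocol 8.4.

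**Working it through.** **Step 1. The plan's own figures.** Inputs: N = 10 and a one-sided 95% exact binomial upper limit (Protocol 10.1, SAP 3.1). For x subjects with an event, the limit is the p that solves P(X ≤ x | n = 10, p) = 0.05, which is the 0.95 quantile of a Beta(x + 1, 10 − x) distribution.

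- x = 0: 1 − 0.05^(1/10) = 0.2589; the plan states 0.26.
- x = 1: 0.3942; the plan states 0.39.
- x = 2: 0.5069; the plan states 0.51.
- x = 3, 4, 5: 0.6066, 0.6965, 0.7776; the plan states 0.61, 0.70, 0.78.

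All six limits reproduce.

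**Step 2. Protocol 8.3 applied to hypothetical records.** Every baseline below is allowed by exclusion criterion 9. CS means clinically significant.

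| Record | Screening | After PDT | Route 1 | Route 2 | Under 8.3 alone |
|---|---|---|---|---|---|
| A | Normal | Grade 2, CS | No, below Grade 3 | Yes, new | AE |
| B | Known Grade 1 | Grade 2, CS | No, below Grade 3 | No, already known | Not reached |
| C | Known Grade 2, not CS | Worse within Grade 2, now CS | No, below Grade 3 | No, already known | Not reached |
| D | Known Grade 1 or 2 | Grade 3 or 4, confirmed where applicable | Yes | Not needed | AE |

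A and B end at the same grade and the same clinical significance, yet only A is reached. The entries for B and C take the novelty condition to refer to the abnormality; the other reading is weighed under the objection.

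**Step 3. The same records under the neighbouring sections.** Sections 8, 8.1 and 8.4.1 set no grade threshold and no novelty condition, so B and C can be recorded under them. Section 8.2 also covers B and C where the abnormality is, or reflects, a pre-existing medical condition; otherwise it is silent. Section 8.3 says when an abnormality should be an AE, without saying that nothing else may be one.

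**Step 4. What the SAP retains.** Laboratory tests are scheduled at Screening, Day 5 and Study Exit. In the shift table a low value that falls further is low-to-low, and a Day 5 change that has resolved by Study Exit does not appear. No laboratory table by CTCAE grade is specified. The change-from-baseline summaries by visit and the individual listings do contain the values, but neither enters AE incidence.

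**Step 5. Size, as illustration only.** The documents give no rate for records like B or C. For one preferred term, with ten subjects in the Safety Population:

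- One missed subject, 1/10 to 0/10: the upper limit goes from 0.3942 to 0.2589, a drop of 0.1353.
- One missed subject, 2/10 to 1/10: from 0.5069 to 0.3942, a drop of 0.1127.

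If each subject had an assumed probability p of such an event, the chance of at least one among ten is 1 − (1 − p)^10: 40% for p = 0.05, 65% for 0.10, 89% for 0.20 and 97% for 0.30. This is the chance that a case arises, not that a site fails to record it.

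**The case against.** The strongest reply is grammatical. Route 2 speaks of a value, and in B and C the clinically significant value was not known before; only a milder one was. On that reading both are AEs and there is no gap. The reading is possible, but it leaves the novelty condition with almost no work to do, since a value first found after consent is nearly always one not known earlier. At best it shows that the sentence can be read in two ways.

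The second reply is that 8.3 is not exclusive. This stands. A reader might infer that 8.3 removes these events from the AE count outright. The documents do not support that: no section tells a site to discard them, and Sections 8, 8.1 and 8.4.1 point toward recording them.

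A reader might also infer a flat contradiction with 8.2. That is too strong. Section 8.2 does not name laboratory values, so the conflict is limited to abnormalities that reflect a pre-existing condition.

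Third, part of the rule is out of view. Section 8.1 refers to a decision flow chart that is not in the available text, and the CRF completion guideline (Protocol 10.2) is a separate document. Either might settle the matter. The SAP also counts events from an NCS page together with AEs. The abbreviation is not expanded in the available text; if it means not clinically significant, that page would not catch a clinically significant worsening.

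Finally, laboratory data are listed among the primary endpoints in SAP 4.1 and remain fully listed, and 8.3 requires the investigator to comment on every out-of-range value. That stands too: the information is kept, though not as an AE.

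**Conclusion.** The point holds as a gap in wording that creates a risk of site-dependent under-recording. It does not show that AEs will be lost or that the primary endpoint is undercounted.

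The conclusion rests on taking the novelty condition to refer to the abnormality, and on a site treating 8.3 as the governing rule for laboratory findings. Both are natural; neither is forced by the text.

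The size cannot be derived from the documents. A reader might infer that each affected subject takes ten points off the AE rate. That is true only for a given preferred term with ten subjects; a subject with any other AE still counts in the any-AE rate. Nor does the number of subjects who enter with a Grade 1 or 2 value measure the number of missed events, and the documents give neither figure.

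**What to change.** In Protocol 8.3, replace the condition at the end of route 2 that limits it to values not known before with *and that is new or has worsened from the pretreatment value*. Keep worsening to Grade 3 or 4 as an AE. Bring the CRF completion guideline into line so that all sites apply the same test.

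This needs no new test or visit and no new SAP analysis, because the added events enter the existing AE tables. The cost is a few more low-grade laboratory AEs and a slightly less favourable reported AE rate.
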